#### 5.2 Secondary analyses

For the primary outcome, we will also use a linear regression (heteroscedastic) to estimate the treatment effect, without adjustment of any covariates but adjusting the therapist random effects.

All secondary continuous outcomes (including the health economic outcomes, EQ-5D-5L index and VAS scores) will be analysed using the linear regression (heteroscedastic) specified in the primary analysis method, with the same adjustment. An unadjusted analysis will also be conducted for each outcome.

We will assess the impact of compliance on outcomes using a CACE (Compliers average causal effect) analysis for the primary outcome. CACE models evaluate the average effect of the intervention in participants who comply with their allocated treatment. This preserves randomisation groups and eliminates introducing any potential confounders introduced by PP analysis.

For categorical outcomes, odds ratio with 95% CI will be reported. We will also plot the data over time, with the mean and confidence intervals, for some of the secondary outcomes such as the International Physical Activity Questionnaire (IPAQ short-form).

#### 5.3 Subgroup analyses

Exploratory subgroup analyses will examine the interaction of treatment assignment with the pre-specified subgroups, including:

- 1. Age group (<65 vs >=65)
- 2. Level of hospital care (Critical care vs Ward)

- 3. Depression (HADS depression score <11 vs >=11)
- 4. Anxiety (HADS anxiety score <11 vs >=11)
- 5. PTSD (IES-r <11 vs >=11)
- 6. Ethnicity (BAME vs non-BAME)
- 7. Wave of pandemic (1st Wave: March 2020, 2nd Wave: September 2020, 3rd Wave: TBC)
- 8. Method of recruitment (NHS digital mailouts vs others)

These subgroup analyses will be conducted in the observed dataset on the basis of ITT population. The analyses will use hierarchical linear regression model with adjustment for covariates in the primary analysis. The overall significance of the interaction will be reported. Estimated treatment difference in each subgroup will be reported with mean treatment difference with 95% CI.

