- 6. PTSD symptom severity: The Impacts of Events Scale-Revised (IES-R) a 22 item self-report measure of difficulties people sometimes face after stressful life events. It has been widely used in studies of survivors of ICU admission, including COVID admissions. It is part of recommended outcomes for studies of respiratory failure survivors [24-26]. A score of ≥11 on the IES-6, an abbreviated version extracted from the longer 22-item IES-R, will be taken to be indicative of case level disorder.
- Depressive and anxiety symptoms: Hospital Anxiety and Depression Scale (HADS). A 14-item questionnaire from which anxiety and depression subscales can be derived. 7 item sub-score values ≥11 points identify case-level anxiety/depression. Commonly used and well validated measure in clinical populations [27].
- 8. Work status: Time lost from work (paid/unpaid) and patient-borne health costs.

- 9. Health and social care resource use: participant self-report and NHS records. The primary health-economic analysis will concentrate on direct intervention and healthcare/personal social services costs, while wider impact (societal) costs will be included within the sensitivity analyses. Participants will complete resource use questionnaires at all follow-up points, to collect resource use data associated with the interventions under examination. We will request a copy of the participant's medical record from their GP at the end of the study follow-up if the participant has not responded to the 12-month follow-up or if we know the participant has died. This will provide information on GP consultations and include copies of any hospital discharge letters allowing us to accurately cost in-patient care costs. Where appropriate we will triangulate data from GP records and participant self-report to achieve a robust estimate of health service activity. Consent will be obtained for access GP records.
- 10. General health Participant self-reported measurements of current overall health and comparison of current health to health 12 months prior.
- 11. Death measured using GP.

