2.8 Randomisation

2.8.1 Randomisation

Pre-randomisation eligibility checks will be carried out to ensure that potential participants meet the eligibility criteria and are not randomised in error. Consent for entry into the study must have been completed prior to randomisation. Subjects will be randomised once they have been registered as eligible for randomisation on the web-based system and completed their baseline questionnaire.

Participants with case level mental health disorder, identified from baseline HADS and IES-6 questionnaires (screening scales for anxiety, depression, PTSD) will be directed to their GP for treatment. This will be included in the PIS. They will continue in the study intervention as long as the REGAIN practitioner and/or the participant consider that their mental health does not preclude engagement with interventions.

Randomisation will be undertaken automatically by the system following completion of the baseline questionnaire using a computer-generated randomisation sequence, performed by minimisation and stratified by:

- 1. age (i. <65; ii. ≥65),
- 2. level of hospital care (i. ICU/HDU; ii. ward),
- 3. case level mental health disorder (i. IES-6 PTSD score ≥11/24 or HADS Anxiety sub-score ≥11/21 or HADS Depression sub-score ≥11/21; ii. IES-6 PTSD score <11/24 and HADS Anxiety sub- score <11/14 and HADS Depression sub- score <11/21).

Participants will be randomised strictly sequentially at study level.

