4. Health utility: Euroqol EQ-5D-5L [10]. Validated, generic HRQoL measure consisting of five dimensions, each with five levels. Each combination of answers can be converted into a health utility score. It has good test-retest reliability, is simple to use, and gives a single preference-based index value for health status that can be used for cost-effectiveness analysis. A statement by NICE highlighted serious concerns regarding the EQ-5D-5L tariffs published by Devlin et al [11]. For that reason, the crosswalk value set will be used to map from the EQ-5D-5L to EQ-5D-3L using previously used and more reliable tariff values. The EQ-5D score ranges from <0-1 where a higher score reflects better quality of life.

5. International Physical Activity Questionnaire (IPAQ short-form). The IPAQ is a wellestablished activity measure reported as metabolic equivalent task (MET)-minutes per week derived from duration of walking, moderate and vigorous exercise [12] The questionnaire will be scored using the IPAQ Scoring protocol

(https://sites.google.com/site/theipaq/scoring-protocol).

6. PTSD symptom severity: The Impacts of Events Scale-Revised (IES-R) a 22 item selfreport measure of difficulties people sometimes face after stressful life events. It has been widely used in studies of survivors of ICU admission, including COVID admissions. It is part of recommended outcomes for studies of respiratory failure survivors [13-15]. The IES-R is scored by summing the response to each of the 22 questions, which each range from 0 (not at all) to 4 (extremely), making a total score range of 0-88. A score of  $\geq$ 11 on the IES-6, an abbreviated version extracted from the longer 22-item IES-R, will be taken to be indicative of case level disorder.

7. Depressive and anxiety symptoms: Hospital Anxiety and Depression Scale (HADS). A 14-item questionnaire from which anxiety and depression subscales can be derived. 7 item sub-score values ≥11 points identify case-level anxiety/depression. The HADs is widely used and a well validated measure in clinical populations [16]. The scores are simply summated to give an anxiety and depression score both ranging from 0-21 where a higher score reflects more severe symptoms of anxiety and depression.

8. Death measured using GP record. Data will be requested from general practices on completion of the trial.

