#### 5.1 Primary analysis

#### 5.1.1 *Primary outcome*

The main analyses will be for overall treatment effect. The primary analysis will use a linear regression (heteroscedastic) model to estimate the treatment effects (95% confidence intervals (CI)), adjusted for baseline as well as adjusted for stratification variables, important patient-level covariates and group effect. The reason for using heteroscedastic model is the variance is different between the arms as the control arm is non-clustered and the intervention arm is clustered [20]. In the trial, the control arm receives individual therapy whereas the intervention arm receives group therapies. The groups or therapist effect will be treated here as random effects. If there is negligible group and centre effect, then the usual linear regression will be used for the analysis.

The main analysis will be carried out on the stratification variables such as:

- Age (continuous)
- Level of hospital care (i. ICU/HDU; ii. ward)
- Case level mental health disorder (i. IES-6 PTSD score ≥11/24 or HADS Anxiety subscore ≥11/21 or HADS Depression sub-score ≥11/21; ii. IES-6 PTSD score <11/24 and HADS Anxiety sub- score <11/21 and HADS Depression sub- score <11/21)

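### SAP 5.3 puts the IES-6 case-level cut-point (11 of 24) on the full IES-R (0-88), so participants without case-level PTSD could enter the PTSD subgroup

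*SAP*

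**What the plan says.** SAP 5.3, item 5, defines the subgroup as "PTSD (IES-r <11 vs >=11". Items 3 and 4 of the same list split HADS depression and HADS anxiety at 11, which is the case-level value that the trial uses for each subscale.

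The other places that give a PTSD threshold attach it to the short form:

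- SAP 2.6.2, item 6, says that a score of 11 or more "on the IES-6, an abbreviated version extracted from the longer 22-item IES-R, will be taken to be indicative of case level disorder". The same item scores the full IES-R separately, "making a total score range of 0-88", and gives no cut-point for it.
- Protocol 2.3.1 has the same rule: "A score of ≥11 on the IES-6, an abbreviated version extracted from the longer 22-item IES-R".
- Protocol 2.8.1 and SAP 2.9 build the minimisation factor on "IES-6 PTSD score ≥11/24", combined by *or* with the two HADS subscales.
- SAP 5.1.1 carries that composite into the primary model as a covariate: "Case level mental health disorder (i. IES-6 PTSD score ≥11/24".
- Protocol 2.9.1 and SAP 2.5.1 also use the IES-6 when they identify case-level participants from the baseline questionnaires.

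Protocol 6.3 names PTSD as an exploratory subgroup but gives neither instrument nor threshold. SAP 5.3 is therefore the only operational definition. SAP 8 records no deviation from the protocol.

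**The concern.** A cut-point has meaning only on the scale it was set for. The same number on a scale with 22 items instead of 6 is a much lower bar, so the subgroup would be labelled PTSD without following the trial's own definition of case-level PTSD.

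Baseline IES-R items are collected and the IES-6 is needed for minimisation, so both scores should be available. Literal code would then run without error and print a plausible interaction estimate. SAP 5.3 also adjusts the subgroup models for the primary-analysis covariates. One model would therefore contain an IES threshold of 11 out of 24 inside the case-level covariate and 11 out of 88 in the interaction.

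At stake is the interpretation of that one interaction and of the two subgroup estimates reported with it.

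**Working it through.** **1. Scales.** SAP 2.6.2 scores each IES-R item 0 to 4. IES-R maximum: 22 × 4 = 88, as stated. IES-6 maximum: 6 × 4 = 24, as stated in Protocol 2.8.1.

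**2. The two thresholds.**

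- IES-6: 11/24 = 45.8% of the maximum; 11/6 = 1.83 points per item.
- IES-R: 11/88 = 12.5% of the maximum; 11/22 = 0.50 points per item.

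The ratio of the per-item bars is 1.83/0.50 = 3.7.

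**3. Direction, without assumptions.** IES-R = IES-6 + the sum of the other 16 items, and no item is negative. So IES-R ≥ IES-6 for every participant, and IES-6 ≥ 11 implies IES-R ≥ 11. No case is lost. In the other direction, a non-case with IES-6 = 10 can have an IES-R of up to 10 + 16 × 4 = 74.

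**4. Size, which needs assumptions.** The documents give no IES distribution for this population. For illustration, assume a one-factor model with 22 exchangeable items scored 0 to 4, six of them serving as the IES-6, loadings of 0.6, 0.7 or 0.8, and category thresholds 0, 0.6, 1.2 and 1.8 on the latent scale (8,000 simulated participants). The overall level is shifted to give each IES-R mean. The share of non-cases (IES-6 < 11) with IES-R ≥ 11 is then:

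| Assumed IES-R mean | Loading 0.6 | Loading 0.7 | Loading 0.8 |
|---|---|---|---|
| 5 | 14.6% | 15.0% | 14.3% |
| 8 | 26.5% | 25.2% | 22.8% |
| 11 | 37.7% | 34.2% | 30.2% |
| 15 | 51.6% | 45.1% | 39.0% |
| 20 | 64.2% | 56.9% | 49.5% |
| 25 | 74.8% | 66.4% | 57.9% |
| 30 | 82.3% | 73.9% | 65.0% |
| 35 | 87.9% | 79.9% | 70.9% |

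The range is about 14% to 88%. The share passes one half at a mean of roughly 15 to 20, depending on the loading. No simulated case was missed, as step 3 requires.

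**5. Dilution in the same model.** Because every case is included, the proportion of true cases in the subgroup as written is p = P(IES-6 ≥ 11) / P(IES-R ≥ 11):

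- mean 5, loading 0.6: 0.006/0.151 = 4%;
- mean 20, loading 0.7: 0.162/0.639 = 25%;
- mean 35, loading 0.8: 0.425/0.833 = 51%.

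Suppose the treatment effect were Δ₁ in cases and Δ₀ in all non-cases. The upper stratum would then estimate pΔ₁ + (1 − p)Δ₀ and the lower stratum Δ₀, so the contrast would be p(Δ₁ − Δ₀), a fraction p of the intended one. If the effect changes gradually with symptom severity, the attenuation will differ.

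**6. With the subgroup on the IES-6.** It equals the PTSD component of the case-level definition, so the number of non-cases in it is zero by construction.

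**The case against.** The strongest reply is that this is a slip of the pen. The item follows two HADS items that use 11, SAP 2.6.2 gives the right rule, and a statistician reading the whole SAP could reconcile the two. The protocol has a comparable slip: Protocol 2.8.1 gives one HADS anxiety limit with denominator 14, where SAP 2.9 has 21. The table shells are in a separate document, so no coding error has been shown. The analysis is also one of eight subgroups that the SAP calls exploratory, and Protocol 6.3 says that they are not powered.

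Most of this stands, and it limits the importance of the point. It does not remove it. The threshold is an operative rule that nothing elsewhere expressly corrects, and SAP 1 binds the reported results to the written plan and asks for deviations to be justified.

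Several stronger readings are tempting but unsupported:

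- *Most non-cases would be moved.* This needs a baseline IES-R mean of roughly 15 to 20 or more under the model above, and the documents give no such figure. For the same reason one cannot say that the comparison becomes nearly symptom-free participants against everyone else.
- *Everyone with an IES-6 of 3 to 10 would be moved.* Equal item means give 0.50 × 6 = 3 on average, but this fails for individuals. IES-6 = 10 with zero on the other 16 items gives IES-R = 10 and is not moved. IES-6 = 0 with 11 points on the other items is moved.
- *The subgroup should match the minimisation factor.* That factor is a composite with HADS anxiety and depression. No PTSD-only subgroup can match it; only its PTSD component can be matched.
- *About 40 of 88 is the right IES-R threshold.* 0.458 × 88 = 40.3 is proportional scaling. It shows the size of the mismatch and is not a validated cut-point.

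**Conclusion.** The contradiction is established from the documents alone: SAP 5.3, item 5, uses the IES-6 threshold on the IES-R, against SAP 2.6.2, 2.9 and 5.1.1 and Protocol 2.3.1 and 2.8.1. The direction of error is also certain. Cases are kept and only non-cases can be misplaced.

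The size is not established. The supportable statement is that an unknown and possibly large share of non-cases would enter the PTSD subgroup. The illustrative 14% to 88% rests on the one-factor model, the chosen loadings and category thresholds, and assumed IES-R means of 5 to 35.

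The consequence is confined to one exploratory interaction. The primary model and the minimisation use the IES-6, and the sample size does not involve the IES at all. The item should be corrected before analysis, but it is not critical to the trial's main result.

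**What to change.** Replace SAP 5.3, item 5, with: PTSD (baseline IES-6 <11 vs ≥11 of 24), scored from the six IES-6 items within the baseline IES-R. Naming baseline makes the timing explicit, which the item now leaves unstated. Check the separate table shells and any analysis code for use of the IES-R total in this subgroup, and align them.

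The cost is one line in a SAP revision and a short code check. No data collection is needed, because the IES-6 is already required for minimisation. The correction is best made and dated before unblinded results are seen, since changing a subgroup definition afterwards would have to be reported and justified as a deviation.

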#### 5.4 Sensitivity analyses

#### 5.4.1 Additional covariate analysis

The sensitivity analysis on the primary outcome will be carried out on the additional variables such as:

- Sex (Male, Female, Other, Prefer not to say)
- BMI (Continuous)
- Ethnicity (White, Black Caribbean, Black African, Black Other, Indian, Pakistani, Bangladeshi, Chinese, Mixed- White and Black Caribbean, Mixed- White and Black African, Mixed- White and Asian, Prefer not to say, Other)\*

#### \* Sex and Ethnicity categories may be grouped together if numbers are too low

#### 5.4.2 Imputed analysis

The primary analysis will be replicated to analyse the imputed datasets. if imputation is deemed appropriate. The pooled results will be reported.

#### 5.4.3 CACE analysis

Also, it is likely that non-compliance will occur (i.e. exercise sessions not attended or participant requests for treatment) during the trial. Careful monitoring of non-compliance will be conducted. If large numbers of treatment non-compliance are observed, Complier-Average Causal Effect (CACE) models or other appropriate methods will be used. The CACE analysis will also be replicated using different definitions of compliance.

#### 5.5 Significance levels and adjustments of p-values for multiplicity

Treatment effects will be presented, with appropriate 95% confidence intervals, for both the unadjusted and adjusted analyses. Tests will be two-sided and considered to provide evidence for a significant difference if p-values are less than 0.05 (5% significance level). All analyses will be conducted as ITT unless otherwise specified. No adjustment of p-values in the analysis as there is no multiple comparison in the analyses.

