6.3 Subgroup analyses

Pre-specified, exploratory sub-group analysis will include age, need for critical care support, depression, anxiety, PTSD and ethnicity. The sub-group effects will be assessed using regression modelling with the interaction term of sub-group and treatment. As the sub-groups are not powered, the results will be reported using 95% confidence intervals.

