#### 2.7 Hypothesis framework

For each of the primary and secondary outcomes, the null hypothesis will be that there is no true difference in treatment effect between the intervention arms.

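### SAP 5.5 denies any multiple comparison and does not confine its p<0.05 rule to the primary, yet the SAP plans at least 26 secondary tests and eight interaction tests; the primary test itself is unaffected

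*SAP*

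**What the plan says.** SAP 5.5 sets one rule for the whole analysis. "Tests will be two-sided", and results are "considered to provide evidence for a significant difference if p-values are less than 0.05". It then states: "No adjustment of p-values in the analysis as there is no multiple comparison in the analyses". Nothing in 5.5 limits the rule to the primary outcome.

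Other sections of the SAP set out what will be tested:

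- **Hypotheses (2.7).** "For each of the primary and secondary outcomes, the null hypothesis will be that there is no true difference in treatment effect".
- **Outcomes (2.6.1, 2.6.2).** The primary is PROPr at three months. PROPr at 6 and 12 months is secondary, and the other secondary scores are measured at 3, 6 and 12 months.
- **Models (5.2).** Every continuous secondary outcome, including the EQ-5D-5L index and VAS, is modelled as the primary is, and each is also analysed unadjusted.
- **Subgroups (5.3).** Eight factors are listed under an exploratory label. "The overall significance of the interaction will be reported", together with a treatment difference and 95% CI in each subgroup.

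Protocol 6.3 lists six subgroup factors, also as exploratory and also assessed through an interaction term, and says: "As the sub-groups are not powered, the results will be reported using 95% confidence intervals". The two factors that appear only in the SAP are wave of pandemic and method of recruitment. SAP section 8 records no deviation from the protocol so far.

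**The concern.** The reason given in 5.5 does not describe the analysis that the SAP plans. One outcome at one time point in two arms involves no multiple comparison, but 5.5 speaks of the analyses as a whole, and 2.7 extends hypothesis testing to every secondary outcome. The SAP marks only the subgroups as exploratory; no sentence says that the secondary outcomes are supportive.

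What is at stake is how the results will be read if PROPr at three months shows no effect. As written, the SAP would let a report describe any secondary score, at any of three times, as showing a significant difference, with no statement that such a result is not confirmatory. Most of these outcomes are self-reported by participants who know whether they attended eight weeks of group sessions or one consultation. Protocol section 10 intends the three-month results to inform practice at once, so this wording has practical weight.

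**Working it through.** **1. The plan's own error budget.** The documents state no family-wise error rate. Their 5% is the type I error in the sample size for the primary comparison. Inputs (SAP 2.8, Protocol 6.1): effect 0.3 SD, 90% power, two-sided 5%, groups of 8, ICC 0.01 in the intervention arm only, 10% loss.

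- Design effect = 1 + 7 × 0.01 = 1.07; allocation ratio = √1.07 = 1.034
- Control arm = (1 + 1.07/1.034) × ((1.960 + 1.282)/0.3)² = 237.5
- Intervention arm = 1.034 × 237.5 = 245.7
- Total = 483.2; 483.2/0.90 = 536.9, against the stated 535 (0.4% apart)

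The sample size therefore reproduces as that of one test at 5%. Nothing below changes it.

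**2. Count of secondary tests (SAP 2.6.2 and 5.2).**

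| Outcome | Times | Tests |
|---|---|---|
| PROPr | 6, 12 months | 2 |
| Dyspnoea, cognitive function, EQ-5D index, EQ VAS, IPAQ, IES-R, HADS anxiety, HADS depression | 3, 6, 12 months | 8 × 3 = 24 |
| **Total** | | **26** |

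This is a minimum. It leaves out death, general health, the PROMIS sub-scales and the unadjusted repeat of each analysis.

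**3. Expected false positives if no effect is real.** 26 × 0.05 = 1.3, whatever the correlation. For the eight interactions, 8 × 0.05 = 0.4.

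**4. Chance of at least one p<0.05 if no effect is real.** Under independence this is 1 − 0.95ⁿ.

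- Secondary: 1 − 0.95²⁶ = 0.736
- Interactions: 1 − 0.95⁸ = 0.337

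Scores from the same people at three times are correlated, so 0.736 is an upper-end figure. The documents give no correlations. The table assumes equally correlated normal test statistics for the 26 secondary tests.

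| Assumed correlation | Chance of at least one |
|---|---|
| 0 | 74% |
| 0.3 | 62% |
| 0.5 | about 47% |
| 0.7 | 32% |

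A second structure, with separate correlations between outcomes and between times, gives similar values: 63% at 0.3/0.5, 49% at 0.5/0.7, 39% at 0.7/0.7 and 29% at 0.8/0.8.

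**5. Subgroups, protocol against SAP.** Protocol 6.3: age, critical care, depression, anxiety, PTSD, ethnicity = 6. SAP 5.3: those six plus wave and recruitment method = 8. Both use an interaction term and report 95% CIs. The SAP adds a report of significance and two factors.

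**The case against.** The strongest reply is that the sentence in 5.5 was meant for the primary comparison, where it is true: two arms, one outcome, one time point. The primary objective is singled out in both documents, and no passage makes a secondary or subgroup result a criterion of success. Reporting is built on estimates with 95% CIs, post-hoc analyses must be labelled as such (SAP section 7), and leaving secondary outcomes unadjusted is accepted practice when they are declared supportive.

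Much of this stands. A reader might infer that the trial's main conclusion has an inflated error rate; it does not. A reader might also infer that a false significant finding among the secondary outcomes is more likely than not. That requires every null to be true and correlation to be modest: at an assumed equal correlation of 0.5 the chance is already slightly below one half. Nor does the SAP abandon the protocol's subgroup plan. It keeps the exploratory label and the confidence intervals, and adds a significance report. Finally, it would be too broad to say that every outcome except death is self-reported, because Protocol 2.3.1 also draws resource use from NHS and GP records.

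The reply does not rescue the text of 5.5. The sentence refers to the analyses in general under a heading on multiplicity, the 0.05 rule has no stated limit, 2.7 sets a null hypothesis for each secondary outcome, and the supportive label that would make unadjusted testing acceptable is missing.

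**Conclusion.** The point holds as an error in the stated rationale and a gap in how secondary results are to be interpreted. The count of at least 26 secondary tests and eight interactions comes directly from the SAP, and so does the expected 1.3 false positives among the 26, given that all nulls are true. The chance of at least one, between 32% and 74% over the correlations tried, depends on that same condition and on assumed correlations. The 34% for the eight interactions assumes independence.

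The primary test keeps its 5% error rate and the sample size of 535 is unaffected. The subgroup part is smaller: a significance report that Protocol 6.3 did not call for, and two added factors that are not recorded as changes. The SAP should be corrected on these points, but no result for the primary question depends on it.

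**What to change.** Changing only the last sentence of 5.5 would leave conflicting text in 5.5, 2.7 and 5.3, so four edits belong together.

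- **SAP 5.5.** Delete the rationale that there is no multiple comparison, and restrict the p<0.05 rule to PROPr at three months. State that secondary outcomes and later time points are supportive and are reported as estimates with unadjusted 95% CIs, without confirmatory significance claims. If a confirmatory secondary claim is wanted, name one or two outcomes now and test them in fixed order after the primary.
- **SAP 2.7.** Limit the hypothesis statement to match.
- **SAP 5.3.** Keep the exploratory label. Report interaction estimates with 95% CIs, in line with Protocol 6.3, in place of overall significance.
- **SAP section 8.** List wave of pandemic and method of recruitment as subgroups added since the protocol.

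The cost is SAP wording only, with no new data and no change in sample size. The downside is that secondary results cannot be called significant, unless they are among any outcomes named for fixed-order testing.
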